## EXTENSION PHASE STATISTICAL ANALYSES

All statistical analyses will be performed by the sponsor or designee. Statistical programming and analyses will be performed using SAS and/or other validated software.

#### DEMOGRAPHICS

Demographic and Baseline characteristics will be summarized. For continuous variables (eg, age, weight) the number of non-missing values, median, mean, standard deviation (SD), and minimum and maximum will be displayed. For categorical variables (eg, gender, ethnicity) the counts and proportions of each value will be tabulated.

#### ANALYSIS OF EFFICACY

Efficacy will be assessed in the Extension Phase with the following:

- Seizure Frequency: Percentage change in 28-day seizure frequency in the Extension Phase compared to baseline. The primary analysis will use data prospectively collected during the 2-week Pretreatment Phase to calculate baseline 28-day seizure frequency. A secondary analysis will use data prospectively collected during the 2-week Pretreatment Phase plus data retrospectively collected during the 4 week period before Visit 1 to calculate baseline 28-day seizure frequency. (revised per Amendment 02)
- Responder Rate: A responder is defined as a subject with a 50% decrease in 28-day seizure frequency during the Extension Phase when compared to baseline. The responder rate will be summarized. Analyses using the 2 different baseline definitions above will be performed.
- Seizure-free status: The proportion of subjects who are seizure-free will be summarized during the Extension Phase
- CGI-C

#### **PHARMACOKINETIC ANALYSES**

Not applicable.

#### PHARMACODYNAMIC ANALYSES

Not applicable.

#### PHARMACOKINETIC/PHARMACODYNAMIC ANALYSES

Not applicable.

#### PHARMACOGENOMIC ANALYSES

Not applicable.

#### ANALYSIS OF SAFETY

The safety of the study population exposed to perampanel will be examined based on nature, frequency, and severity of AEs, chemistry and hematology laboratory test results, vital signs, and 12-lead ECG abnormalities over the treatment period. Any potential safety signal will be explored by analysis of safety data by dose achieved in the study.

#### EXTENT OF EXPOSURE

Duration of Extension Phase exposure will be calculated as the number of days between the date the subject received the first dose of study drug and the date the subject received the last dose of study drug in the Extension Phase.

Overall Extension Phase compliance rate for each subject will be calculated as the mean compliance rate over all the visits.

#### Adverse Events

Adverse events will be classified into standardized medical terminology from the verbatim description (investigator term) using the Medical Dictionary for Regulatory Activities (MedDRA). Adverse events will be presented by preferred term nested within SOC. Verbatim description and MedDRA level terms, for all AEs will be contained in the data listings of the clinical study report for this protocol.

The TEAEs will be summarized by age group and by EIAED and non-EIAED groups. The incidence of TEAEs will be reported as the number (percentage) of subjects with TEAEs by SOC and PT. A subject will be counted only once within an SOC and PT, even if the subject experienced more than 1 TEAE within a specific SOC and PT. The number (percentage) of subjects with TEAEs will also be summarized by maximum severity (mild, moderate, or severe) and by relationship to study drug (Yes [related] and No [not related]).

Adverse events of special interest will also be summarized by SOC and PT using MedDRA SMQ terms.

A subject data listing will be produced for all deaths, SAEs, and discontinuation due to an AE.

The number (percentage) of subjects with treatment-related TEAEs will be summarized by SOC and PT. Treatment-related TEAEs include those events considered by the investigator to be related to study treatment. The number (percentage) of subjects with treatment-related TEAEs will also be summarized by maximum severity (mild, moderate, or severe).

Treatment-emergent adverse events are defined as:

- Adverse events that emerge during treatment, having been absent at pretreatment (Baseline)
- Reemerge during treatment, having been present at Baseline but stopped prior to treatment

• Worsen in severity during treatment relative to the pretreatment state, when the AE is continuous

#### LABORATORY VALUES

Clinical laboratory values will be evaluated for each laboratory parameter by subject. Descriptive summary statistics (eg, mean, standard deviation, median, minimum, maximum) for the laboratory parameters and changes from baseline (Visit 1) to the last visit in the Extension Phase (Follow-up Visit, Week 56) will be summarized by cohort and overall.

Laboratory test results will be assigned a low/normal/high (LNH) classification according to whether the value was below (L), within (N), or above (H) the laboratory parameter's reference range. Shift tables will be used to compare the baseline (Visit 1) LNH classification to the LNH classification at end of study.

Clinical laboratory results post-baseline will be evaluated for markedly abnormal values. Appendix 1 presents the Sponsor's Grading for Laboratory Values that will be used to identify subjects with markedly abnormal laboratory values. For the incidence of markedly abnormal laboratory values, each subject may be counted once in the laboratory parameter value high and in the laboratory parameter low categories as applicable.

#### VITAL SIGNS

Vital sign values will be evaluated on an individual basis by subject. Abnormal vital sign values will be identified as those outside (above or below) the reference range, where appropriate. Reference ranges for vital sign parameters will be included in the clinical study report for this protocol. Descriptive summary statistics (eg, mean, standard deviation, median, minimum, maximum) for vital sign parameters and changes from baseline (Visit 2) to each visit and to the last visit in the Extension Phase (Follow- up Visit, Week 56) will be evaluated for each cohort and overall.

#### ECG RESULTS

For 12-lead ECG parameters, changes from baseline (Visit 1) to the last visit in the Extension Phase (Follow-up Visit, Week 56) will be summarized for each cohort and overall.

QTc (QTcF) and PR variables will also be analyzed to include a summary of the following:

- Number of subjects with QTc in the borderline or abnormal category (430-450 msec, >450 msec, and >500 msec) during treatment, and
- Number of subjects with an increment of 30-60 msec and > 60 msec from baseline (Visit 1).

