The end of the study will be the date of the last study visit for the last subject.

The maximum total duration of treatment for each subject will be 52 weeks and the maximum total duration of the study for each subject will be 58 weeks (2 weeks Pretreatment+52 weeks of treatment+4 week Follow-up). (revised per Amendment 02)

Subjects who complete the Extension Phase and who, in the opinion of the investigator, will likely continue to demonstrate a positive benefit-to-risk ratio from treatment with perampanel may be enrolled into an extended access program (EAP) for perampanel if EAP is implemented for this age group in the country where the subject resides. (revised per Amendment 02)

An overview of the study design is presented in Figure 1.

a: Subjects to receive study treatment starting at Week 0 of the Treatment Phase through Week 52 of the Extension Phase.

b: Follow-up Period Visit is to be completed at the end of the Treatment Phase for those subjects not rolling over to the Extension Phase of the study, for those subjects who early terminate from the study, and for all subjects completing the Extension Phase.

c: Prior to entry into the Maintenance Period, subjects have been maintained on their last Titration Period dose for at least 2 weeks.

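### Extension ECG and lab change from baseline, and the final vitals change, end at the off-treatment Week 56 visit, where no ECG or vitals are scheduled

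*Protocol*

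**What the plan says.** The Extension analyses are described in Protocol Appendix 3. For ECG the rule is: "For 12-lead ECG parameters, changes from baseline (Visit 1) to the last visit in the Extension Phase (Follow-up Visit, Week 56) will be summarized". No other visit is named for the summary of ECG change values. For labs it is: "changes from baseline (Visit 1) to the last visit in the Extension Phase (Follow-up Visit, Week 56) will be summarized by cohort". The lab shift table has a different end point: "Shift tables will be used to compare the baseline (Visit 1) LNH classification to the LNH classification at end of study". For vitals the text asks for "changes from baseline (Visit 2) to each visit and to the last visit in the Extension Phase", and again identifies that last visit as Follow-up, Week 56.

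The same appendix states that no study drug is given in the Follow-up Period. Footnote b of Tables 6 and 7 places the visit 4 weeks ± 6 days after the last dose. It exempts subjects who switch to commercial perampanel or enter the extended access program (EAP), who have a telephone contact instead.

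SAP 3 and 5.9 limit the supplied SAP to the Core Study and leave the Extension to a separate SAP.

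**The concern.** Long-term safety is a secondary objective, and the Extension carries treatment to Week 52. A change-from-baseline summary meant to describe that period should end on treatment, at a visit where the measurement is taken. The named visit fails the second condition for ECG and vitals, and the first for labs.

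Followed literally, the ECG change-value table and the last vitals row would be empty or filled by unplanned recordings. The lab change table would describe children at least three weeks off study drug, leaving out those who moved to commercial supply or the EAP. On-treatment ECGs, vitals and labs are collected, but the text does not direct the ECG and lab change summaries to them.

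**Working it through.** **1. Schedule against analysis text.** The table uses Protocol Tables 6 and 7, plus Core Tables 4 and 5 for Visit 8 (non-EIAED) or Visit 9 (EIAED). Footnote f of the Core tables counts that visit as the first Extension visit for subjects who continue.

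| | Visit 8/9 | Week 28/32 | Week 40/44 | Week 52 | Follow-up, Week 56 | Early Discontinuation |
|---|---|---|---|---|---|---|
| Labs | yes | yes | yes | yes | yes | yes |
| Vitals | yes | yes | yes | yes | **no** | yes |
| ECG | yes | yes | no | yes | **no** | yes |

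Scheduled on-drug occasions up to Week 52 are therefore 4 for labs, 4 for vitals and 3 for ECG. At Week 56 only one of the three assessments is scheduled. The Core Follow-up column in Tables 4 and 5 does mark vitals and ECG, so the blanks are specific to the Extension.

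**2. Timing.** The tables use Day = 7 × week + 1. Week 52 gives 7 × 52 + 1 = 365 and Week 56 gives 7 × 56 + 1 = 393, both as printed. The gap is 393 − 365 = 28 days. With ± 6 days, the visit falls 22 to 34 days after the last dose.

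**3. Drug remaining.** Fraction left = 2^(−24d / t½), with d in days and t½ in hours.

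Protocol 9.4.1 gives a half-life of about 25 h with an EIAED and 105 h without. Protocol 9.4.4 reports preliminary clearance in subjects under 24 months without an EIAED at about 40% of that in older subjects. Assumption: if volume is unchanged, half-life scales as 1/clearance, so 105 / 0.4 = 262.5 h.

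| Days after last dose | 105 h | 262.5 h (assumed) |
|---|---|---|
| 22 | 528/105 = 5.03 half-lives, 3.1% | 528/262.5 = 2.01 half-lives, 25% |
| 28 | 672/105 = 6.40 half-lives, 1.2% | 672/262.5 = 2.56 half-lives, 17% |
| 34 | 816/105 = 7.77 half-lives, 0.5% | 816/262.5 = 3.11 half-lives, 12% |

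At 25 h, 28 days is 672/25 = 26.9 half-lives, so effectively nothing remains.

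**4. On-treatment window.** SAP 8.2.2 ends the on-treatment period for labs, vitals and ECG 14 days after the last dose. That rule is written for the Core Study. If it were carried over, the earliest Follow-up Visit would lie 22 − 14 = 8 days outside it.

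**5. The lab shift table.** Protocol 9.1 defines the end of the study at trial level: "The end of the study will be the date of the last study visit for the last subject". That date cannot serve as a subject's end point, so the shift table needs a subject-level one. Reading it as the subject's own last visit would lead back to Follow-up, but the text does not say so.

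**The case against.** **The on-treatment safety picture survives.** This largely stands. Appendix 3 still examines "vital signs, and 12-lead ECG abnormalities over the treatment period". QTc categories are counted during treatment, and the same section also lists "Number of subjects with an increment of 30-60 msec and > 60 msec from baseline (Visit 1", which is itself a change-from-baseline summary not tied to Week 56. Vitals are summarised at each visit, and markedly abnormal labs do not depend on Week 56. A reader might infer that Extension ECG change goes unanalysed, or that long-term safety signals would be missed. The documents do not support that. What is affected is the summary of ECG change values, the final vitals change, and the lab change and shift.

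**Protocol 9.7.1.8 may already cover the Extension.** It asks for lab change by visit and to the last on-treatment value, and for ECG change by visit. It is not expressly limited to the Core Study. This is arguable, since Appendix 3 has its own safety text. Even on the wide reading, Appendix 3 still contradicts its own schedule.

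**The Extension SAP governs and has not been seen.** It may already use a different end point. That limits how firmly one can predict the final tables, but it does not reconcile the protocol text.

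**Selection.** A reader might infer that Week 56 labs are biased because EAP entrants are children judged "will likely continue to demonstrate a positive benefit-to-risk ratio from treatment with perampanel may be enrolled into an extended access program (EAP"). Entry also depends on whether such a program exists for the age group in the subject's country. The approved ages in Protocol 7 start at 4 or 12 years, which may limit commercial switching. The share exempt is not stated and could lie anywhere from none to all completers. Neither the direction nor the size of any bias can be derived.

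**Washout.** A reader might take Week 56 as a drug-free state. Under the clearance assumption, some drug may remain in the youngest non-EIAED subjects. The point rests on dosing having stopped, not on complete elimination.

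**Conclusion.** The conflict within Appendix 3 is real. For ECG change values and the final vitals change, the named visit has no scheduled measurement in either table. For labs, the named visit is 22 to 34 days after the last dose and omits every subject exempt from Follow-up, so the result describes a post-treatment subset of unknown size. Drug remaining at 28 days is about 1.2% at 105 h, or about 17% (12% to 25% over the visit window) under the assumed 262.5 h; the conclusion does not depend on which applies.

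The consequence is moderate. These are descriptive summaries of a secondary objective, the on-treatment data are collected, and the categorical ECG and lab summaries remain. It should be corrected because, as written, one summary cannot be produced from scheduled data and another describes the wrong period. The verdict assumes that the Extension SAP, which was not available, has not already changed the end point.

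**What to change.** In Appendix 3, and in the Extension SAP if it does not already do so:

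- End the change from baseline for labs, vitals and ECG at end of treatment, defined as the last on-treatment value. That is Week 52 or Early Discontinuation, where all three are scheduled in both tables.
- Summarise labs and ECG by visit as well, following Protocol 9.7.1.8, and keep the by-visit vitals.
- Use the same end-of-treatment point in the lab shift table instead of the trial-level term.
- Report Follow-up labs separately as post-treatment, with the number of subjects contributing.
- Adopt the Core SAP window of last dose plus 14 days for the Extension, so that both phases use one definition of on-treatment.

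The cost is wording in Appendix 3 and possibly in the Extension SAP. No visit, sample or assessment is added.

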## **OTHER ANALYSES**

## Growth

Descriptive summary statistics of changes from baseline in height and weight will be evaluated for each cohort and overall. This data will be compared with normative scores to assess clinical relevance.

Changes from baseline for thyroid function and IGF-1 testing will be summarized.

2 LIST OF ABBREVIATIONS AND DEFINITIONS OF TERMS

Abbreviation	Term
AE(s)	adverse event(s)
AED	antiepileptic drug
ALT	alanine aminotransferase
AST	aspartate aminotransferase
ATC	anatomical therapeutic class
BMI	body mass index
BP	blood pressure
CGI	Clinical Global Impression
CGIC	Clinical Global Impression of Change
CGIS	Clinical Global Impression of Severity
DMC	Data Monitoring Committee
ECG	Electrocardiogram
eCRF	electronic case report form
EIAED	enzyme-inducing antiepileptic drugs
EOT	End of treatment
FAS	Full Analysis Set
IGF-1	insulin-like growth factor-1
LLN	lower limit of normal
LNH	low/normal/high
LOCF	last observation carried forward
MedDRA	Medical Dictionary for Regulatory Activities
PD	Pharmacodynamics
РК	Pharmacokinetics
PT	preferred term
QTc	corrected QT interval (time from the beginning of the QRS complex to the end of the T wave, corrected for heart rate)
SAE	serious adverse event
SAP	statistical analysis plan
SAS	Safety Analysis Set
SD	Standard Deviation

Abbreviation	Term
SI	Système International
SMQ	standardized MedDRA queries
SOC	system organ class
TEAE	treatment-emergent adverse event
TEMAV	treatment-emergent markedly abnormal laboratory values
TLG	tables, listings, and graphs
ULN	upper limit of normal
WHO DD	World Health Organization Drug Dictionary

3 INTRODUCTION

The purpose of this statistical analysis plan (SAP) is to describe the procedures and the statistical methods that will be used to analyze and report results for the core study of Eisai Protocol E2007-G000-238 in pediatric subjects from 1 month to less than 4 years of age with epilepsy. The statistical methods for the Extension Phase will be described in a separate SAP.

3.1 Study Objectives

3.1.1 Primary Objective

To evaluate the pharmacokinetics (PK) of perampanel during the Maintenance Period of the Core Study following oral suspension administration given as an adjunctive therapy in pediatric subjects from 1 month to less than 4 years of age with epilepsy.

3.1.2 Secondary Objectives

- To evaluate the short- and long-term safety and tolerability of perampanel oral suspension, given as an adjunctive therapy, in subjects from 1 month to less than 4 years of age with epilepsy
- To evaluate the long-term effect of perampanel oral suspension, given as an adjunctive therapy, on growth from baseline to end of treatment in pediatric subjects from 1 month to less than 4 years of age with epilepsy

3.1.3 Exploratory Objective

The exploratory study objective was to explore the short- and long-term efficacy of perampanel oral suspension, given as an adjunctive therapy, in subjects from 1 month to less than 4 years of age with epilepsy as assessed by:

- Percent change in 28-day seizure frequency during the Titration + Maintenance Periods compared to baseline and during the Extension Phase compared to baseline
- Proportion of subjects with a 50% decrease in 28-day seizure frequency during the Maintenance Period compared to baseline and during the Extension Phase compared to baseline
- Proportion of subjects who are seizure-free during the Maintenance Period and during the Extension Phase
- Clinical Global Impression (CGI) of change (CGI-C)

[figure not shown]

b: Follow-up Period Visit is to be completed at the end of the Treatment Phase for those subjects not rolling over to the Extension Phase of the study, for those subjects who early terminate from the study, and for all subjects completing the Extension Phase.

e: Prior to entry into the Maintenance Period, subjects have been maintained on their last Titration Period dose for at least 2 weeks.

4 DETERMINATION OF SAMPLE SIZE

Study E2007-G000-238 used population PK modeling to determine PK in pediatrics ≥ 1 to <24 months of age and from 2 to less than 4 years of age and compared these data to PK in adolescents and adults. In Study E2007-G000-232, data were obtained in 42 pediatric subjects ≥ 2 to <12 years of age, with approximate equal numbers enrolled in the age ranges of ≥ 2 to ≤ 6 and ≥ 7 to <12 years.

Given the narrower age range planned for Study 238 compared with Study 232, and the fact that the PK data from this study would be pooled with the data from subjects ≥ 2 to <12 years of age, it was proposed that PK data obtained in at least 16 subjects ≥ 1 to <24 months of age would be adequate to characterize the PK in this age group. In addition, Study 238 PK data in at least 16 subjects in this age group would account for more than 25% of the data obtained for perampanel overall in subjects ≥ 1 month to <12 years of age, confirming appropriate assessment and representation of this age group in the overall assessment of PK and safety in the pediatric population. The sample size was to be increased to at least 24 subjects if dose-normalized (to 8 mg) exposure in the Maintenance Period from the first 16 subjects in this study was not comparable to existing data in subjects aged ≥ 2 to 18 years.

5 STATISTICAL METHODS

All descriptive statistics for continuous variables will be reported using mean, standard deviation (SD), median, minimum and maximum. Categorical variables will be summarized as number (percentage) of subjects. All summaries will be performed by age cohort (1 to ≤ 6 months, > 6 to ≤ 12 months, >12 to < 24 months, and ≥ 24 to <48 months) and overall, unless stated otherwise.

5.1 Study Endpoints

5.1.1 Primary Endpoint

The primary endpoint of this study is to evaluate PK of perampanel during the Maintenance Period of the Core Study following oral suspension administration given as an adjunctive therapy in pediatric subjects from 1 month to less than 4 years of age with epilepsy, using a population PK approach. Details regarding PK analysis will not be described in this SAP but will be described in a separate analysis plan.

5.1.2 Secondary Endpoints

Secondary endpoints are safety and tolerability endpoints including incidence of treatmentemergent adverse events (TEAEs) and serious adverse events (SAEs), clinical laboratory parameters, vital signs, ECG parameters, and growth parameters (height, weight, head circumference, thyroid function, and IGF-1 levels).

5.1.3 Exploratory Endpoints

The efficacy endpoints are:

- Seizure frequency: Percent change in 28-day seizure frequency during the Treatment Phase and during the Extension Phase, compared to baseline.
- Responder rate: Proportion of subjects with a 50% decrease in 28-day seizure frequency during the Maintenance Period and during the Extension Phase, compared to baseline.
- Seizure-free rate: Proportion of subjects who are seizure-free during the Maintenance Period and during Extension Phase.
- Clinical Impression of change (CGI-C) at the end of core and extension phase.

5.2 Study Subjects

5.2.1 Definitions of Analysis Sets

The Safety Analysis Set (SAS) is the group of subjects who received at least 1 dose of study drug and had at least 1 postdose safety assessment.

The **Full Analysis Set (FAS)** is the group of subjects who received study drug, had seizure frequency >0 during baseline period and had any seizure frequency data during the Treatment Phase.

The **Modified Full Analysis Set (Modified FAS)** is the group of subjects who received study drug and had any seizure frequency data during the Treatment Phase.

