#### CLINICAL GLOBAL IMPRESSION OF CHANGE

The CGI will be used to evaluate perceived seizure frequency and severity, the occurrence of AEs, and overall functional status of the subject. The evaluations of CGIS and CGIC both use a 7-point scale. For the CGI-S, 1 = normal, not at all ill and 7 = extremely ill, and for the CGI-C, 1 = very much improved and 7 = very much worse.

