### 9.7.1.2 Definitions of Analysis Sets

The Pharmacokinetic Analysis Set is the group of subjects with at least 1 PK assessment of perampanel during the Maintenance Period with a documented dosing history.

The Safety Analysis Set is the group of subjects who received at least 1 dose of study drug and had at least 1 postdose safety assessment.

The Full Analysis Set (FAS) is the group of subjects who received study drug and had any seizure frequency data during the 2 weeks of Pretreatment Phase plus 4 weeks before the Pretreatment Phase and during the Treatment Phase.

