5.4 Exploratory Efficacy Analyses

This study is designed to assess PK and provide safety, tolerability and efficacy data in children with epilepsy aged 1 month to less than 4 years. Given the small sample size and lack of placebo or comparator, it will not be possible to draw definitive conclusions regarding the efficacy of perampanel oral suspension for the population in this study. As such, no formal statistical tests will be performed. Summary statistics will be displayed for all efficacy parameters in the Full Analysis Set unless stated otherwise.

The primary analysis will use data from the Pretreatment Phase to calculate baseline 28-day seizure frequency. A secondary analysis will use data from the Pretreatment Phase plus data from the 4 weeks prior to Visit 1 to calculate baseline 28-day seizure frequency. Seizure frequency will be based on the number of seizures per 28 days, calculated as the number of seizures over the time interval multiplied by 28 and divided by the number of days in the interval. Seizure frequency will refer to the overall seizure type, unless stated otherwise, obtained by combining across all seizure types.

Post-baseline data reported only during the **on-treatment** duration will be analyzed. The on-treatment duration is defined as follows:

• For diary data: The duration between the day of first study drug dose and the last

day of study drug dose, inclusive.

• For CGIC data: The duration after the day of first study drug dose up to 7 days after the last study drug dose, inclusive.

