5.4.3 Other Exploratory Efficacy Analyses

The percent change in 28-day seizure frequency during the Titration Period (no imputation) and Maintenance Period (using LOCF-type imputation described in Section 5.3.5) will also be summarized.

Percent change, seizure free and responder rate in 28-day seizure frequency analyses will also be repeated for each seizure type, as appropriate for subjects who have that seizure type during the baseline. Subjects who develop new seizure types during the study will be summarized by seizure type separately.

CGI-C scores at EOT compared to baseline will be summarized using frequency table. The EOT value is the last non-missing value while on treatment.

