7 CHANGES IN THE PLANNED ANALYSES

There are no major changes in the planned analyses from the protocol at the time of the finalization of this SAP.

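### The SAP's Full Analysis Set requires baseline seizures above zero, and by default this removes children without baseline seizures from the CGI-C table, where the protocol keeps them

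*SAP*

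**What the plan says.** **Protocol.** Section 9.7.1.2 (and the synopsis) places a treated child in the FAS if the child "had any seizure frequency data during the 2 weeks of Pretreatment Phase plus 4 weeks before the Pretreatment Phase" and also during the Treatment Phase. No minimum count is set. Section 9.7.1.6 lists CGI-C among the parameters summarised in that FAS. Section 9.5.1.3 describes the scale broadly: "The CGI will be used to evaluate perceived seizure frequency and severity, the occurrence of AEs, and overall functional status of the subject".

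**SAP.** Section 5.2.1 keeps the name FAS but limits it to the "group of subjects who received study drug, had seizure frequency >0 during baseline period", again with Treatment Phase seizure data. It adds a Modified FAS, which "is the group of subjects who received study drug and had any seizure frequency data during the Treatment Phase", with no baseline condition. Section 5.4 sets the default: "Summary statistics will be displayed for all efficacy parameters in the Full Analysis Set unless stated otherwise". Section 5.1.3 lists CGI-C among the efficacy endpoints. Section 5.4.3 says only that "CGI-C scores at EOT compared to baseline will be summarized using frequency table". Section 5.4.1 uses the Modified FAS for seizure-free status and nothing else. Section 7 states: "There are no major changes in the planned analyses from the protocol".

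**The concern.** The above-zero condition has a clear purpose for two endpoints. Percent change cannot be computed from a baseline of zero, and a 50% reduction from zero cannot be achieved. CGI-C has no such denominator: it is a 7-point global rating that also takes in adverse events and function. Carrying the condition over to CGI-C drops children for a reason that does not apply to that endpoint.

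An analyst following the SAP would report a CGI-C distribution on a different set of children from the one the protocol specifies, under the same set name and with no note of the difference. The study is small and its results are shown by age cohort. The minimum cohort sizes for children under 24 months are 6, 5 and 5, so in a cohort of 5 each child is 20 percentage points.

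**Working it through.** The documents give no figure to reproduce here. The check is a comparison of texts, followed by two illustrations on assumed inputs.

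**1. Which set does CGI-C use?**

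| Condition | Protocol FAS | SAP FAS | SAP Modified FAS |
|---|---|---|---|
| Received study drug | yes | yes | yes |
| Baseline seizure data | any, zero included | frequency above zero | none required |
| Treatment Phase seizure data | yes | yes | yes |
| CGI-C summarised here | yes (9.7.1.6) | yes (5.4 default) | no |

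The link from CGI-C to the SAP FAS rests on the default in 5.4, and nothing in 5.4.1 to 5.4.3 overrides it for CGI-C. A zero counts as data: SAP 8.1.2 treats a diary day answered No as a valid seizure count.

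**2. Can such children be enrolled?** Yes. Inclusion criterion 5 asks for at least one seizure before Visit 1 and sets no time window; the revision history shows that Amendment 01 removed a 4-week limit.

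**3. Which baseline window applies?** SAP 5.2.1 does not say. SAP 8.1.1 defines two baselines: the 2-week Pretreatment Phase, and those 2 weeks plus the preceding 4. SAP 5.4.1 runs percent change and responder rate on the subset of the FAS with Pretreatment Phase data. That subset would be largely redundant if FAS membership already required Pretreatment seizures, so the 6-week window is the more natural reading.

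**4. How many might be affected?** Assume Poisson seizures at rate r per 28 days, so P(zero) = exp(−r × days/28). The rates are assumptions.

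| r per 28 days | 42 days | 14 days |
|---|---|---|
| 1 | exp(−1.5) = 22% | exp(−0.5) = 61% |
| 2 | exp(−3) = 5% | exp(−1) = 37% |
| 4 | exp(−6) = 0.2% | exp(−2) = 14% |

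Variation in rates between children raises P(zero) for a given mean rate. Children with frequent seizures bring it close to nil.

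**5. What could it do to the CGI-C result?** Take 24 children with CGI-C data (assumed).

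- Suppose 4 have a zero baseline and half of the other 20 improve. The SAP FAS gives 10/20 = 50%. With all 24 included, the share runs from 10/24 = 41.7% (none of the 4 improved) to 14/24 = 58.3% (all 4 improved).
- Suppose 2 have a zero baseline and half of the other 22 improve. The SAP FAS gives 11/22 = 50%, and the full range is 11/24 = 45.8% to 13/24 = 54.2%.

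The range lies on both sides of 50%, so the definitions alone do not fix the direction.

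**The case against.** The strongest reply is that little depends on this table. CGI-C sits under other exploratory analyses, no test is planned, SAP 5.4 disclaims definitive efficacy conclusions, and the study is primarily pharmacokinetic. The number of children affected could be zero. All of this stands and sets the severity.

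A reader might go further and infer that the exclusion inflates the improved share and hides worsening. The documents do not support that.

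- **Direction.** A child with no baseline seizures has less room for seizure improvement, so an upward shift from excluding such children is plausible. But the scale also covers adverse events and function, on which these children can improve or worsen.
- **Harm.** SAP 5.6 runs all safety analyses on the Safety Analysis Set, which has no seizure condition. Adverse events by severity and relationship, serious events, discontinuations and events of special interest, including status epilepticus and convulsions, remain visible for these children. Seizure-free status is also reported on the Modified FAS. What is lost is their global rating.

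A reader might also infer that SAP 7 denies any change. It denies only major ones, and whether a narrower set for an exploratory table is major is a matter of judgement. The omission is one of documentation.

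Finally, the Modified FAS is not identical to the protocol FAS: it requires no baseline data. Both still require Treatment Phase seizure data. The choice between them should therefore be stated in the SAP.

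**Conclusion.** The point holds on the text. The SAP narrows the FAS, its default rule carries the narrowing to CGI-C, and the protocol summarises CGI-C in a set without that condition. Eligible children with no seizures in the baseline period drop out of the CGI-C table for a reason that belongs to percent change and responder rate.

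The size is uncertain. For assumed Poisson rates of 1 to 4 per 28 days, the chance that a child is excluded is 22% down to 0.2% on the 6-week baseline, or 61% down to 14% on the 2-week baseline. The finding holds under either window; only the count changes. The effect on the improved share is of unknown sign. Severity is low, since the endpoint is exploratory and descriptive, but following the SAP can give a different result from the protocol's and the correction is small.

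**What to change.** - **SAP 5.4.3:** state that CGI-C is summarised in the Modified FAS.
- **SAP 5.2.1:** say whether the baseline period means the 2-week Pretreatment Phase or the 6 weeks. Keep the above-zero condition for percent change and responder rate, where the denominator needs it.
- **SAP 7:** record that the FAS is narrower than the protocol's and that a Modified FAS has been added.

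The cost is one phrase, one definition and one entry. The Modified FAS already exists and no new data are needed. The drawback is that the CGI-C table would have a different denominator from percent change and responder rate, so its title should name the set.
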